Sponsor

Bergen University

Movement analysis of the sacroiliac joint part of the

Indication and treatment of adult spinal deformity

The INTRAKS-study

09.12.2020

Movement of the Sacroiliac (SI) Joint, comparing conventional RSA with the Sectra Implant Movement analysis using a low dose CT for high accuracy measurement

Abstract

Background: Radiostereometric analysis (RSA) is a high precision *in vivo* measuring method and regarded as the gold standard for motion analysis. RSA has been around for over 40 years and its accuracy is properly evaluated. The CT technics have evolved and now low dose CT scans can reproduce 3-D models of bone and joints. The Sectra Implant Movement analysis (IMA) is a new method using a low dose CT for high accuracy measurement. There is no study evaluating the precision and accuracy of the new CT based method. We want to compare the accuracy of the two methods.

Method/design: The RSA method will be tested in patients that already have tantalum markers inserted around the SI joints from earlier studies conducted at Ullevål University Hospital. There are two patients in the age of 40-50 years available for RSA analysis with and without provocation of the SI joints. Some are fused in one SI joint after insertion of the tantalum markers, but the contralateral joint can then be used for the analysis. At the same time, we will perform low dose CT with and without provocation of the SI joints. The results of the analysis will be compared.

Discussion: The conventional RSA is an invasive method using tantalum markers inserted in to bone. If the CT method has the same accuracy, then the tantalum markers will become obsolete and future studies can easily be performed using non-invasive low dose CT scans.

Keywords: RSA, CT method, low dose CT, IS joint, movement

Introduction:

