Because of the high accuracy and precision, radiostereometric analysis (RSA), has become a well-established method for three-dimensional (3-D) measurements of micro motion in joints [1-6]. The implantation of tantalum markers is invasive, but no reports of patient injuries are reported. The markers might be inserted through the approach used during a surgical intervention or in an extra stab incisions in the skin to get the markers to the necessary position in the bony structures. The placements of the markers are of outmost importance to achieve good quality measurements. At least three non collinear markers in each segment and a good distance and distribution in all three axes (X, Z, Y) is essential for a good 3-D configuration.

The CT techniques have evolved and now low dose CT scans can reproduce 3-D models of bone and joints. The Sectra Implant movement analysis (IMA) [7-10] is a non-invasive method using a low dose CT scan. No tantalum markers are needed and joint provocation can easily be conducted in the CT. The CT scan is then sent to the Sectra AB for analysis.

Method:

Patients and methods:

The RSA method will be tested in patients that already have tantalum markers inserted around the SI joints from earlier studies [11, 12], approximately five years ago, conducted at Ullevål University Hospital. These are patients with long lasting severe sacroiliac joint pain. There are two patients in

the age of 40-50 years available for RSA analysis with and without provocation of the SI joints, at the same time we will perform low dose CT with and without provocation of the SI joints. For the non-provocation, the patient will be in a supine-position. The provocation x-ray/low dose CT will be performed; 1: anterior straight legraise 2: One side figure of four position, both with 1kg of load. Some are fused in one SI joint after insertion of the tantalum markers, but the contralateral joint can then be used for the analysis. We will also measure eventual movement in the fused joint and the symphysis (if tantalum markers present). The Center for Implant and Radiostereometric Research Oslo has extensive experience with RSA and established state of the art measuring method of movement in the SI joint. They will perform the RSA measurements. The CT scan is send to the Sectra AB for analysis.

Statistical analysis:

Null hypothesis (H0): There is no difference in the accuracy

Alternate Hypothesis (H1): There is a difference in the accuracy

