Continuous variables will be described with mean and standard deviation\, and the normality of the data will be checked using the histograms, QQ-plots and the Kolmogorov-Smirnov-Test of normality. The differences of motion will also be tested for normality. The paired sample T-test will be used to detect possible significance in the difference between the two groups. Non-parametric tests are used if the assumption of normality does not hold. All analysis will be conducted using commercially available software (SPSS version 24, IBM Inc.) and the level of significance is set to $p < 0.05$ in a two-sided test.

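### The normality check that picks the test is almost uninformative at 2 to 4 pairs, and the rank test it can switch to cannot reach p < 0.05 at that size

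*Combined protocol and SAP*

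**What the plan says.** In the Combined protocol and SAP, the Statistical analysis section states that "the normality of the data will be checked using the histograms, QQ-plots and the Kolmogorov-Smirnov-Test of normality". The next sentence extends the check to the differences of motion. The paired t-test is the default, and then: "Non-parametric tests are used if the assumption of normality does not hold". The level is 0.05 "in a two-sided test".

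The section gives no cut-off for the check and does not say whether the check on the raw data or the one on the differences triggers the switch. It names no non-parametric test, does not choose between exact and asymptotic p-values, and gives no number of pairs.

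The size of the data set follows from Patients and methods: "There are two patients in the age of 40-50 years available for RSA analysis with and without provocation of the SI joints". The manoeuvres are "1: anterior straight legraise 2: One side figure of four position, both with 1kg of load", each set against a supine position without provocation. On usable joints: "Some are fused in one SI joint after insertion of the tantalum markers, but the contralateral joint can then be used for the analysis". Movement in the fused joint, and in the symphysis where markers exist, is also to be measured.

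The null hypothesis is that accuracy does not differ. The Discussion paragraph of the Abstract says that equal accuracy for CT would make tantalum markers unnecessary.

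**The concern.** A switch based on a normality check is sensible only if the check can detect a relevant departure and the fallback test can detect a real difference. With two patients, both are in doubt.

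The consequence is one-sided. The result most likely to be read as support for CT is non-rejection of the null hypothesis. If the data go to a test whose smallest possible p-value exceeds 0.05, non-rejection is certain however large the CT error. Because the check uses plots without a stated criterion, that choice can be made after the RSA-CT differences are known.

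**Working it through.** The plan has no sample-size, power or pair-count figure to reproduce, so the check starts from the design.

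**1. Number of pairs.** Inputs: 2 patients, 1 or 2 unfused joints each, 2 manoeuvres. Assumption: one value per joint per manoeuvre.
- Unfused joints: 2 × 1 = 2 up to 2 × 2 = 4, so 2 to 4 pairs per manoeuvre.
- Both manoeuvres pooled: 2 × 2 = 4, 2 × 3 = 6 or 2 × 4 = 8 pairs.
- Pooling three axes as well: 12, 18 or 24. Fused joints and the symphysis could add more.

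**2. What the K-S test can see** (mean and SD estimated from the sample).
- With 2 values, the standardised values are always ±1/√2 = ±0.707. Then D = Φ(0.707) − 0.5 = 0.760 − 0.500 = 0.260 for every data set, so there is no information.
- Simulated power (200,000 samples per case, cut-off set to a 5% false-alarm rate):

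| Pairs | Exponential | Lognormal |
|---|---|---|
| 3 | 7% | 8% |
| 4 | 11% | 16% |
| 5 | 14% | 20% |
| 8 | 24% | 37% |

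- With the standard K-S cut-off, not adjusted for estimated parameters, no sample of 6 or fewer was flagged for any distribution tried.

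**3. Smallest two-sided p the fallback can give.** The most extreme result has all differences of one sign.
- Exact signed-rank and exact sign test: p = 2/2ⁿ.
- Asymptotic signed-rank: z = [n(n+1)/4] / √[n(n+1)(2n+1)/24]. At n = 4, z = 5/√7.5 = 1.83; at n = 5, z = 7.5/√13.75 = 2.02.

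| Pairs | Exact (either test) | Signed-rank, asymptotic, uncorrected | Signed-rank, asymptotic, continuity-corrected |
|---|---|---|---|
| 2 | 0.50 | 0.180 | 0.371 |
| 3 | 0.25 | 0.109 | 0.181 |
| 4 | 0.125 | 0.068 | 0.100 |
| 5 | 0.0625 | 0.043 | 0.059 |
| 6 | 0.031 | 0.028 | 0.036 |
| 8 | 0.0078 | 0.012 | 0.014 |

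At 4 or fewer pairs the signed-rank test cannot reject under any of the three calculations, and the exact sign test cannot either. The one exception found is an uncorrected normal approximation to the sign test: z = (n/2)/(√n/2) = √n, which at n = 4 is 2.00, p = 0.0455. With continuity correction, z = (2 − 0.5)/1 = 1.5 and p = 0.134. At 5 pairs the answer depends on the p-value method. From 6 pairs the signed-rank test can reject under all three calculations.

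**4. What the rule costs if only K-S drives it.** Simulation with 4 independent normal pairs, adjusted 5% cut-off, and an exact rank test (which never rejects at this size) when flagged. Offsets are in SDs of the paired difference; they are illustrative, since the plan gives no SD or expected error.

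| True offset | t-test always | Rule with K-S switch |
|---|---|---|
| 1 SD | 29% | about 27% |
| 2 SD | 76% | about 72% |
| 3 SD | 97% | about 92% |

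The loss is roughly the 5% false-alarm rate applied to the t-test's rejections: 0.97 × 0.95 = 0.92.

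**The case against.** A reader might infer that one branch of the rule always returns no difference. The documents do not support that. They never fix the number of pairs, and pooling both manoeuvres over 3 or 4 joints gives 6 or 8 pairs, at which a rank test can reject. This objection stands, with the qualification that the plan does not specify such pooling and that the pairs would be clustered within two patients, so a p-value computed as if they were independent would not be valid.

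A reader might also set 97% rejection for the t-test against 0% for the exact rank test at 4 pairs and a 3 SD offset, and take that as the harm done by the rule. It compares the two tests, not the rule. Because K-S seldom fires, the K-S-driven loss is about 5 percentage points or less, and nil with the unadjusted cut-off. A larger loss needs a judgement from the plots, and how often that would occur is unknown.

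Nor is it right that normality is checked only on raw motion, which a paired test does not require to be normal. The section says the differences are tested too, and that is the relevant check. What remains is that the plan does not say which result triggers the switch.

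Finally, the larger problems are the two patients and any reading of non-rejection as sameness. Both survive removal of the switch. The statement about markers is a conditional in the Abstract, not a formal decision rule. These points lower the priority of this one but do not answer it.

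**Conclusion.** The point holds in conditional form and should be fixed, although it is secondary to the sample size. With 2 to 4 pairs the normality check cannot do its job: no information at 2 pairs, and 11% to 16% power against strong skew at 4. If 4 or fewer pairs are analysed, a signed-rank test (exact or asymptotic) or an exact sign test cannot reach two-sided p < 0.05. At 5 pairs an exact test cannot (0.0625), but an uncorrected asymptotic signed-rank p can (0.043). At 6 or more pooled pairs rejection is possible, but the pairs are not independent.

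The practical risk is less the K-S test than an unspecified reading of histograms and QQ-plots, made with the differences in view, that moves the analysis to a test unable to reject and so favours a conclusion of equal accuracy.

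This rests on one value per joint per manoeuvre and on the fallback being a signed-rank or sign test, neither of which the plan states. The simulated rejection rates also assume independent, normally distributed differences.

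**What to change.** In Statistical analysis:

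- Delete the normality check as a means of choosing the test, together with the sentence "Non-parametric tests are used if the assumption of normality does not hold".
- Prespecify one analysis of the paired RSA-CT differences: the mean difference with its t-based 95% confidence interval, with the definition and number of pairs stated.
- List every RSA value, CT value and difference by patient, joint and manoeuvre.
- If a rank test is kept, make it a named sensitivity analysis with an exact p-value. State that with 5 or fewer pairs it cannot reach 0.05 and that its non-significance is not evidence of equal accuracy.

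The cost is a few sentences and a short listing, with no new patients or measurements. Normality would be assumed rather than checked, but at this size it cannot usefully be checked. The interval will be wide: its half-width is t/√n SDs of the difference, which is 3.18/√4 = 1.6 SD at 4 independent pairs and 12.71/√2 = 9.0 SD at 2. Detection stays weak too: with one pair per patient the t-test rejects in only 26% of samples at a 3 SD offset. The change removes a discretionary step; it does not remove the limits of having two patients.
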